**Multilevel HPV Self-Testing Intervention for the Increase of
Cervical Cancer Screening among Women in Appalachia**

NCT04411849

June 30, 2023

1. Introduction / Overview

The overall P01 program titled “Take CARE: Improving Uptake of Cervical Cancer Prevention Services in Appalachia” is a series of three projects that will be implemented within health systems across four states in Appalachia. All three are designed to work in tandem and are focused on reducing the cancer burden in Appalachia through health system-based interventions, but each has a specific focus. Project 1 focuses on reducing cigarette smoking in adult female smokers who are considering quitting through counseling and nicotine replacement therapy. Project 2 is designed to improve HPV vaccination rates among 11-12 year olds and 13-26 year olds through educational and promotional materials and Electronic Health Record reminders. Project 3 seeks to improve cervical cancer screening rates. Project 3 will be described in detail in this protocol.

Most cases of cervical cancer occur among unscreened and underscreened women.^{1,2} Current screening guidelines from the United States (US) Preventive Services Task Force and other organizations recommend women ages 30-65 should receive a combination of cytology (i.e., Pap test) and a clinic-based HPV test every 5 years, a clinic-based HPV test alone every 5 years, or cytology alone every 3 years.³ However, nearly 20% of age-eligible women in the US are not within guidelines.⁴ Strategies to increase screening among these women, including HPV self-testing, have therefore been identified as the most important cervical cancer screening research priority.⁵

HPV self-testing involves women using a device to collect their own cervicovaginal sample for HPV testing. International work has shown that up to about 40% of unscreened and underscreened women who are sent an HPV self-test in the mail will use the test at home and return it by mail (i.e., mail-based HPV self-testing).⁶⁻¹⁵ As a result, multiple countries (e.g., the Netherlands and Australia) recently integrated mail-based HPV self-testing into their national screening programs.^{16,17} In the US, focus group and survey studies have shown that most women would be willing to use an HPV self-test (i.e., high acceptability), and recent pilot studies, including our own work, have established the feasibility of mail-based HPV self-testing programs.¹⁸⁻²⁴

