Given the emergence of HPV self-testing, there is a need to examine the effectiveness and implementation of large mail-based HPV self-testing programs in the US. In doing so, it is critical to identify strategies that may increase women’s return of a mailed HPV self-test and receipt of follow-up care, if needed. One promising strategy is patient navigation (PN). PN is a patient-centered healthcare delivery model that provides education and support to help people overcome concerns and barriers to care.²⁵ In past research, PN has repeatedly increased cancer screening behaviors, including cervical cancer screening, and receipt of follow-up care.²⁶⁻²⁹ Thus, it is important that PN be examined for helping women use/return an HPV self-test and receive follow-up care, if needed. Many of the most common concerns and barriers reported by women about using an HPV self-test are modifiable and include: concerns about using the test incorrectly; uncertainty about test accuracy; and worry about returning a test by mail.^{9,22,30,31} However, very little is known about PN in the context of HPV self-testing.

The proposed project will evaluate a multilevel cervical cancer screening intervention centered around HPV self-testing via a delayed intervention trial. The intervention will include mail-based HPV self-testing (patient-level), healthcare provider education sessions about HPV self-testing (provider-level), and PN for women who do not initially return their HPV self-test or who subsequently test positive for a high-risk (i.e., oncogenic) HPV infection (system-level). The intervention will be part of a P01 cervical cancer prevention program implemented in clinics within health systems in Appalachia, a geographic region with cervical cancer disparities.

2. Specific Aims

Specific aims will address each outcome type (service, implementation, and client outcomes) recommended for implementation research.³²

Aim 1 (service outcomes): Determine the effectiveness of the intervention in increasing cervical cancer screening (primary outcome). Hypothesis 1a: The intervention will increase screening among unscreened and underscreened Appalachian women who are ages 30-64. Further, PN will increase HPV self-test return among

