women who are initially non-returners. Screening will be defined as: a) return of an HPV self-test and negative for a high-risk HPV infection; b) return of an HPV self-test, positive for a high-risk HPV infection, and attendance at a follow-up appointment; or c) receipt of a clinic-based test (e.g., Pap test). Hypothesis 1b: The increase in screening will be similar across patient characteristics.

Aim 2 (implementation outcomes): Assess the fidelity, sustainability, and cost-effectiveness of the intervention. Hypothesis 2a: We hypothesize that the intervention will be implemented with high fidelity and sustained by the clinics/health systems. Hypothesis 2b: We also hypothesize that the intervention will be a cost-effective strategy for increasing cervical cancer screening.

Aim 3 (client outcomes): Determine satisfaction with the intervention at the patient- and provider-levels. Hypothesis 3a: Women will report high levels of satisfaction with HPV self-testing (if HPV self-test is returned) and PN (if received). Hypothesis 3b: Healthcare providers will report high levels of satisfaction with the provider education sessions and have improved knowledge, attitudes, and beliefs about HPV self-testing.

[figure not shown]
3. Methods

Overview

We will examine the effectiveness and implementation of the multilevel intervention using a delayed intervention trial (Figure 1). The methodology for this study will draw heavily upon our recently completed pilot study of a mail-based HPV self-testing program (IRB# 2015C0036).²⁴ Further, this study will build upon the formative work currently being done for this P01 program under IRB# 2019C0169. The study described in this protocol will involve a Group Randomized Trial (GRT). In GRTs, identifiable groups are randomized to a treatment condition with measurements taken on members from those groups to assess the impact of the intervention. In this project, health systems will be randomized to one of two study arms (Group 1 will be the Early Intervention and Group 2 will be the Usual Care Continued/Delayed Intervention). Please note that similar to IRB# 2015C0036, the intervention will be referred to as “The HOME (Health Outcomes through Motivation and Education) Project” or simply as the “HOME Project”.

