To prepare PNs for the GRT, members of the project team will lead PN training activities. Modeled after our past PN work,³⁴ training may include both a review of general PN principles and project-specific training. General PN principles may include training on keeping relationships professional with patients, potential ethical issues (e.g., confidentiality), and how to work as a link between patients and the clinic. Project-specific training may include detailed information about the project and how to: a) provide information in an understandable format about HPV, cervical cancer, and screening (including self-testing); b) interpret HPV testing results and discuss the results; c) address patients' likely concerns, barriers, and questions; d) help patients set goals and plans for screening; e) provide social support; f) compile a list of potential local resources (e.g., transportation systems); and g) complete project forms.

Specific training activities may include case studies, content reading, role-playing, and mock interactions with patients. During training, we will stress how to: provide information about HPV, cervical cancer, and screening, with a focus on Appalachian disparities; describe the effectiveness of HPV self-testing; and address women's concerns/barriers. For social support, PNs will be trained to provide support that is informational (i.e. trusted source of information), emotional (e.g., supportive listening, expressing concern, etc.), and instrumental (e.g., help with transportation, etc.). PNs will apply these skills when interacting with patients during the randomized trial (as described below). However, during training, there will be no interaction with actual patients or human subject involvement of any kind.

Provider Education Sessions

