Women who have not returned their HPV self-test within two weeks of the device being sent will receive PN for self-test return. PNs will attempt to contact these initial non-returners by text message and/or telephone, making up to 10 attempts at different times and on different days, including weekends. If no contact is made after the final attempt, PNs will send women a letter asking them to contact the PNs (see Appendix). Using a similar approach, PNs contacted almost 90% of participants in our past work.³⁴ During interactions with participants, PNs will apply their training to provide information about HPV and self-testing, address women's concerns and barriers to using/returning their self-test, help women set goals and plans for using/returning their self-test, and provide social support. PNs will also ask women if they need a replacement device sent. To ensure consistency in the process, PNs will use developed guides/scripts during calls and text messages (see Appendices). If a woman has already returned her self-test by the time of contact, the PN will ask if she had any questions. Members of the study team will not have direct contact with any of the participants, only the PNs (who are employees of the clinics) will contact participants or have access to participants' contact information.

PNs will contact each of these initial non-returners at least once about using/returning their self-test, with additional contacts as needed (e.g., if PNs need to locate further information after the first contact). This will allow PNs flexibility that is tailored to each woman's needs. Following completion of PN (or final contact attempt without success and a letter sent), we will give women two additional weeks to return their HPV self-test. All women who do not return their self-test following this additional time will be classified as having not returned their HPV self-test.

HPV Testing

All returned HPV self-tests will be sent to a laboratory at Atila BioSystems (Mountain View, CA) for HPV testing. The laboratory has expertise in HPV testing and has performed this type of testing extensively in the past. Testing will use the Atila AmpFire HPV test, which produces one of the following outcomes for each sample: (a) positive for high-risk HPV type 16 or 18; (b) positive for a high-risk HPV type other than type 16 or 18 (i.e., type 31, 33, 35,

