The patient-level effectiveness outcome and primary outcome for our project will be whether or not women get "screened" during the project. There are three ways a woman can be considered "screened." The first is to return their HPV self-test and test negative for high-risk HPV types. The second is to return their HPV self-test, test positive for high-risk HPV types, and then attend a follow-up appointment at their health system. We are requiring these women to attend a follow-up appointment to be considered "screened" given their HPV infection. The third way is to receive a clinic-based screening test (e.g., Pap test), regardless of HPV self-test return status. This will most likely apply to women in Group 2 health systems during the Usual Care Continued phase, but past studies have shown that some women will get a Pap test after receiving an HPV self-test in the mail (without using the self-test).⁴² All women not meeting one of these three criteria will be considered "unscreened." To determine this outcome, we will examine HPV self-test return status, HPV testing results, and EHR data (follow-up appointment attendance, Pap testing, etc.) for each sampled woman.

Among women who return their HPV self-test, we will examine the timing of device return and categorize each as returned within two weeks of distribution (i.e., prior to any PN) or after two weeks of distribution (i.e., following PN). We will also examine HPV testing results (positive or negative for high-risk HPV types) and collect data from EHR on the number of normal and abnormal clinic-based cervical cancer screening tests received by each woman and any cervical abnormalities found (i.e., low-grade squamous intraepithelial lesion, etc.).

To assess if the intervention is equitable (Figure 4), we will examine patient characteristics via data from HER (e.g., age and when their most recent clinic-based cervical cancer screening test prior to project entry occurred [if

ever]). Lastly, to assess safety, we will examine data from the patient satisfaction survey to see if women report any issues about using their HPV self-test. We do not anticipate such reports to be common, as HPV self-test devices have been used safely and easily by women in several research studies.⁶⁻¹⁵

Sample Size

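### The two-week label can over-credit patient navigation, and the planned share of late returners has no comparison without navigation, so it cannot show that navigation increased self-test return

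*Combined protocol and SAP*

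**What the plan says.** The PN half of Hypothesis 1a (Specific Aims, Aim 1) is a claim about effect: "Further, PN will increase HPV self-test return among", with the target group given as "women who are initially non-returners". It is repeated under Aim 1 (Service Outcomes).

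The section Patient Navigation for HPV Self-Test Device Return sets out the procedure. Its entry rule is: "Women who have not returned their HPV self-test within two weeks of the device being sent will receive PN for self-test return". Navigators then try to reach each woman by text or telephone, "making up to 10 attempts at different times and on different days, including weekends". The section foresees a woman who has already sent her test back when she is reached. It also foresees women who are never reached: "If no contact is made after the final attempt, PNs will send women a letter asking them to contact the PNs". They then have two more weeks to return the test.

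Aim 1, Measures, sorts returned tests by time alone, as "returned within two weeks of distribution (i.e., prior to any PN) or after two weeks of distribution (i.e., following PN". Secondary Analyses then takes, among women who returned a test, the proportion who did so after receiving PN. It presents the result as informative about what PN adds to return. No other analysis addresses that question.

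**The concern.** There are two separate problems.

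- **The label.** A return after two weeks is not necessarily a return after PN. The protocol's own contact procedure allows late returns made before any attempt, and late returns from women who were never reached. Any error from this source favours PN.
- **The inference.** To say what PN added, one must know or estimate how many initial non-returners would have returned without it. The planned share supplies no such figure, and it leaves women who never returned out of the denominator.

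The share is above zero whenever any woman returns late, prompted or not. A stated hypothesis could therefore be reported as supported by a number that would be positive even if PN had no effect.

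**Working it through.** **The plan's own figures.** The plan gives no expected late-return share, PN effect or power for PN. Its power statement (at least 90%) comes with outcome rates only for the Year 2 comparison, 30% versus 10%. With 600/5 = 120 women per health system and an ICC of 0.017, the design effect is 1 + 119 × 0.017 = 3.023. The effective n is 600/3.023 = 198.5 per group and power is 99.9% (normal approximation). That statement is met and is not in question.

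**Is there a comparison without PN?** Self-tests to be mailed, from the Year 2 to Year 5 sections:

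- Group 1: 600 + 100 + 100 + 100 = 900
- Group 2: 0 in Year 2 (a reminder letter and information sheet only), then 100 + 100 + 100 = 300
- Total: 1,200. Adding the 600 Group 2 women of Year 2 gives 1,800, the stated project total.

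Delayed Intervention and Bundling repeat the Year 2 process, and in Sustainability the clinics run PN themselves. Initial non-returners are therefore assigned PN for all 1,200 tests.

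**Does the share track the hypothesis?** Assume 600 tests mailed and late return fixed at 10% of initial non-returners:

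| Early returns | Late returns | Planned share | Return among initial non-returners |
|---|---|---|---|
| 60 | 0.10 × 540 = 54 | 54/114 = 47% | 10% |
| 120 | 0.10 × 480 = 48 | 48/168 = 29% | 10% |
| 180 | 0.10 × 420 = 42 | 42/222 = 19% | 10% |

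The share moves with early return while the quantity in the hypothesis stays the same. The counts are assumed and only illustrate the denominator.

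**What would the share be with no PN effect?** Assume exponential return times and a total window of 28 to 56 days (14 days, then 0 to 4 weeks of PN, then 14 days). The late share is (F(W) − F(14))/F(W), where F(t) is the proportion returned by day t and W is the window. With a median return time of 14 days, F(14) = 0.50.

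- W = 28: (0.75 − 0.50)/0.75 = 33%
- W = 56: (0.9375 − 0.50)/0.9375 = 47%

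With a 7-day median the range is 20% to 25%. The documents give no return times, so these are illustrations.

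**What can late returns bound?** If PN deters no return, the returns due to PN lie between zero and the number of late returns. For example, suppose 180 of 600 women return and half do so late (both assumed). The returns due to PN could then be anywhere from 0 to 90, or 0 to 15 percentage points of the tests mailed.

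**How many women might never be reached?** The protocol cites contact with almost 90% in past work and says that "up to about 40% of unscreened and underscreened women who are sent an HPV self-test in the mail will use the test at home". If all of that return came within two weeks, 600 × 0.60 = 360 women would be initial non-returners; if none did, 600. With about 10% not reached (an assumption carried over), this gives about 36 to 60 women in Group 1 in Year 2, as a floor because the cited rate is slightly below 90%.

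**The case against.** The strongest defence is that the late class is an assignment label. At two weeks every non-returner enters PN, and women never reached still had attempts and a letter, so calling their later return post-PN is loose but arguable. This stands in part: it narrows the no-contact component. It does not cover returns made before any attempt, and it provides no comparison.

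A second defence is that Secondary Analyses speaks of receipt of PN, which may mean actual receipt, and promises only to examine a proportion. That is fair. However, the only rule defined is the two-week cut, and the accompanying sentence still draws an inference about added benefit. The satisfaction survey asks why women did or did not return the test, which helps description but gives no counterfactual.

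Some stronger readings are tempting, but the documents do not support them.

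- *The two-week clock is undefined, or could restart with a replacement device, so the error could run either way.* The PN section counts from the sending of the device, and Fidelity treats distribution as a mailing. The early class is glossed as before any PN, which a device re-sent during a PN call cannot satisfy. A resample after an inadequate specimen follows a return that has already been made.
- *The 36 to 60 women are mislabelled returns.* They are women not contacted; how many of them return a test is unknown and could be none.
- *The share gives no information.* It describes the timing of returns and supports the bound above.

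**Conclusion.** The concern holds as a point about one secondary analysis. The two-week label can over-credit PN. By how much cannot be derived, because the documents give neither return times nor the timing of the first attempt; the pre-contact part is zero if contact is immediate at two weeks.

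The inferential gap depends on none of the assumed figures. With PN assigned to every initial non-returner and no self-tests in Group 2 in Year 2, the planned share cannot estimate what PN added or show that it increased return. Its denominator also does not match the population of Hypothesis 1a.

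A reader might infer that the main result is affected. It is not: the definition of screened does not use the two-week category, so the Group 1 versus Group 2 comparison stands. The change should be made because it alters what the trial can say about PN, at almost no cost.

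**What to change.** 1. In Aim 1, Measures, rename the late class *returned after two weeks (PN-eligible)*.
2. In Secondary Analyses, report the proportion returning among all women with no return at two weeks. This needs only mailing and return dates.
3. Where contact dates are recorded, break down the numerator of that proportion into: returned before any PN attempt; returned after attempts or a letter without contact; returned after successful contact. Apply the split to the numerator only, because the first class contains returners by definition. Do not compare rates by contact status as if causal, since being reachable may itself go with returning.
4. Replace the added-benefit sentence with a statement that the result is descriptive.
5. In Specific Aims and in Aim 1 (Service Outcomes), state that the PN half of Hypothesis 1a is examined descriptively and not tested.

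The cost is wording in these sections and a weaker claim for PN. Contact-date fields may also have to be added to the PN form. Training of Patient Navigators says that navigators learn to "complete project forms", but the documents do not show whether those forms record contact dates. The design, sample size and primary analysis do not change.
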